6.6.2. Reversibility Analysis

Reversibility will be summarized separately for each sperm parameter that met a pre-specified sperm parameter decrease. The number (percent) who met reversibility criteria and the cumulative number (percent) who met reversibility criteria at each Monitoring Phase visit will be presented.

Reversibility for subjects meeting pre-specified sperm parameter decrease threshold[s] at Week 13 will be displayed by double-blind treatment group; at Week 26 by treatment sequence and responder/non-responder at Week 13; and at/after Week 39 by actual treatment sequence. For the Week 26 interim analysis, an additional reversibility table for “completers” (ie, subjects who have completed the full 52 weeks of off-study drug follow-up, met reversibility criteria, or prematurely discontinued from study while being followed in the monitoring phase) will be produced if at least 1 subject has an evaluable monitoring phase visit and is ongoing in the monitoring phase at the time of data cutoff.

No formal testing or CI is planned. A by-subject data listing of semen data (with measurement where reversibility criteria was met flagged) will be provided for subjects who entered the Monitoring Phase.

Table 6-3 shows an example for hypothetical proportions of subjects (at final analysis) with reversed sperm concentration by monitoring visit number and double-blind treatment group for subjects with a $\geq 50\%$ decrease at/prior to Week 13.

Table 6-3. Hypothetical Proportion of Subjects Who Met Reversibility Criteria for Sperm Concentration by Treatment Group and Monitoring Phase Visit (Subjects with a $\geq 50\%$ Decrease in Sperm Concentration at/prior to Week 13)

Treatment before Monitoring	Monitoring Visit 1	Monitoring Visit 2	Monitoring Visit 3	Monitoring Visit 4	Reversibility in Monitoring Phase
Filgotinib	3 / 5	1 / 2	1 / 1	0 / 0	5 / 5
Cumulative Rate	3 / 5 = 60.0%	4 / 5 = 80.0%	5 / 5 = 100.0%	5 / 5 = 100.0%	5 / 5 = 100.0%
Placebo	3 / 6	1 / 3	1 / 2	0 / 1	5 / 6
Cumulative Rate	3 / 6 = 50%	4 / 6 = 68%	5 / 6 = 83.3%	5 / 6 = 83.3%	5 / 6 = 83.3%

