## DEFINITION OF TERMS

Monitoring Phase	A subject who experiences a $\geq 50\%$ decrease in sperm concentration, and/or motility, and/or morphology at any time after 13 weeks will start the Monitoring Phase. Semen samples will be collected every 13 weeks starting from their entry into the Monitoring Phase, for up to 52 weeks or until Reversibility is met, whichever is achieved first.
Arthritis Responder	For RA, PsA, AS or nrAxSpA - improvement in physician's global assessment (PhGADA) of at least 20% compared to Baseline (Day 1) at the specified assessment time
Arthritis Non-responder	For RA, PsA, AS or nrAxSpA, a subject who does not fulfill the definition of Arthritis Responder at the specified assessment time point (refer to Appendix 2 )
Pre-specified decrease threshold	A $\geq 50\%$ decrease in sperm concentration, and/or motility, and/or morphology in comparison to Baseline (Screening). The mean of values for each of the sperm parameters (measured from 2 separate semen samples) will be used in all analyses. Samples will be collected within a 14-day period and with an ejaculation-free period of $\geq 48$ hours and $\leq 7$ days.
Reversibility	Reversibility is met when all semen parameter(s) qualifying the subject to enter into the Monitoring Phase return(s) to greater than 50% of Baseline (ie, to greater than $[0.50 \times \text{mean of 2 sperm collections collected at the Screening visit (ie, Baseline)}]$ ).
Week 13	The Week 13 Study Visit occurs once a subject completes 13 weeks of blinded study drug, and is inclusive of all study assessments performed at the clinic visit and the semen sample collection visits associated with this time point.
Week 26	The Week 26 Study Visit occurs once a subject completes 13 weeks of open-label filgotinib or Standard of Care treatment during the Extension Phase, and is inclusive of all study assessments performed at the clinic visit and the semen sample collection visits associated with this time point.
Standard of Care	Locally approved treatment, accepted by medical experts as a proper treatment for rheumatic conditions, prescribed according to best clinical practice, with no known testicular toxicity. Standard of Care will be reimbursed by the sponsor until the Week 156 visit of the Extension Phase or until a subject completes the Monitoring Phase.

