#### **8.1.4. Exploratory Endpoints**

The exploratory endpoints are:

- Percent of subjects who achieve reversibility among subjects who experience a  $\geq 50\%$  decrease in sperm concentration, and/or motility, and/or morphology
- Change from Baseline in sex hormones, including LH, FSH, inhibin B, and total testosterone at Weeks 13 and 26
- PK characteristics for filgotinib and its metabolite GS-829845

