#### **8.5.3. Exploratory Analyses**

The exploratory analyses of sex hormones will use the same analysis methods used as for the continuous secondary endpoints. For reversibility, the number and percentage and cumulative number and percentage of subjects who achieve reversibility will be displayed by sperm parameter and monitoring phase visit for those subjects with a  $\geq 50\%$  decrease in the sperm parameter(s) qualifying them for entry into the monitoring phase.

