- Subjects with a decrease of $\geq 50\%$ in sperm concentration and/or motility and/or morphology from baseline while on double-blind treatment or open-label filgotinib will have study drug stopped and an investigator selected standard of care treatment that meets protocol-specified criteria started. Subjects meeting a sperm decrease while on standard of care in extension phase will continue on a standard of care regimen. Semen samples will be collected off-study drug/control (eg, standard of care in extension phase) every 13 weeks during the Monitoring Phase until reversibility is met or for up to 52 weeks, whichever occurs first. Reversibility is met when all sperm parameter(s) qualifying the subject to enter the Monitoring Phase return to greater than 50% of the baseline value (ie, greater than $0.5 \times$ [mean of 2 evaluable samples collected at the screening visit]). Data will be summarized for each sperm parameter meeting a pre-specified sperm decrease threshold at the visit when study drug was stopped. The number (percent) who met reversibility criteria and the cumulative number (percent) who met reversibility criteria at each Monitoring Phase visit will be presented separately for subjects who met pre-specified sperm parameter decreases at Week 13 (summarized by double-blind treatment group); for subjects meeting pre-specified sperm parameter decrease thresholds at Week 26 (summarized by treatment sequence and rheumatic disease responder/ non-responder status at Week 13) and at or after Week 39 (summarized by treatment sequence).

For the safety analyses, subjects will be grouped by double-blind treatment group (ie, filgotinib 200 mg or placebo) for safety events reported during the double-blind phase of the study.

Safety events reported during the extension phase will be summarized by treatment sequence (double-blind filgotinib to open-label filgotinib, double-blind filgotinib to standard of care, and placebo to standard of care).

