Note for programming: Subjects who started standard of care in extension phase and met a sperm decrease threshold at a visit other than “LT Week 156” will be considered to be prematurely discontinued from this phase for “Pre-Specified Decrease in Sperm Parameters”. For subjects who started standard of care in extension phase, did not go into the monitoring phase, and did not complete study, the reason for premature discontinuation of study will be used for reason for early termination of extension phase. Subjects who started standard of care in extension phase and completed the study (without going into monitoring phase) will be considered to have completed the extension phase of the study on standard of care.

Monitoring Phase Completion Status

- Completed Monitoring Phase of study
 - Met Reversibility criteria for all sperm parameters meeting pre-specified sperm decrease threshold[s]
 - Completed 52-weeks of off-treatment follow-up
- Continuing Monitoring Phase of study (for interim analysis only, represents those who remain under observation in the Monitoring Phase at the time of data cutoff date)
- Did not complete Monitoring Phase and reason for premature discontinuation

Note for programming: Reasons for Early Termination from Monitoring Phase and Completion of Monitoring Phase will be pulled from the Study Completion eCRF.

Study Completion Status

- Completed study
- Ongoing in Study (for interim analysis only, includes subjects currently participating in the study at the time of an interim analysis)
- Did not complete study with reasons for premature discontinuation of study

For the status of study drug, study completion and reasons for premature discontinuation of study drug or study, the number and percentage of subjects in each category will be provided. The denominator for the percentage calculation will be the total number of subjects in the Safety Analysis Set who entered into the study phase for the column being summarized.

The number of subjects screened for the study that did not meet eligibility criteria will be summarized overall and by inclusion/exclusion criteria not met (multiple reasons may be marked for an individual screen). Subjects who were rescreened will be summarized based on their last chronologic screening attempt. Screens that did not fail ≥ 1 eligibility criteria but were not randomized will be summarized by the reason the subject was not randomized.

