6.6. Exploratory Endpoints

6.6.1. Definition of the Exploratory Endpoints

The exploratory endpoints are:

- Percent of reversibility among subjects who experience a $\geq 50\%$ decrease in sperm concentration, and/or motility, and/or morphology
- Change from baseline in hormones, including LH, FSH, inhibin B, and total testosterone at Weeks 13 and 26

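### Reversibility is defined per subject, but SAP 6.6.2 tabulates it only per sperm parameter, so the reversibility analysis does not display the exploratory endpoint as defined (minor)

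*SAP*

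**What the plan says.** **Definition.** Both documents define reversibility for the subject. Protocol, Definition of Terms: "Reversibility is met when all semen parameter(s) qualifying the subject to enter into the Monitoring Phase return(s) to greater than 50% of Baseline". SAP 3.2: "Reversibility is met when all sperm parameter(s) qualifying the subject to enter the Monitoring Phase return to greater than 50% of the baseline value". SAP 1.2 gives the same rule for leaving the Monitoring Phase.

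**Endpoint.** Protocol 8.1.4 words it as "Percent of subjects who achieve reversibility among subjects who experience a" decrease of at least 50% in concentration, motility and/or morphology. SAP 6.6.1 has "Percent of reversibility among subjects who experience a" decrease in the same three parameters. Each is one percentage across the three parameters.

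**Analysis.** Protocol 8.5.3 says the counts and percentages "will be displayed by sperm parameter and monitoring phase visit". SAP 6.6.2 says "Reversibility will be summarized separately for each sperm parameter that met a pre-specified sperm parameter decrease". SAP 3.2, in the same bullet as the all-parameter definition, says "Data will be summarized for each sperm parameter meeting a pre-specified sperm decrease threshold at the visit when study drug was stopped". The only layout shown, SAP Table 6-3, is for sperm concentration alone.

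**Subject-level output elsewhere.** The Monitoring Phase completion status in SAP 4.1 has a category for men who met the criteria on all their qualifying parameters. It is reported as a number and a percentage of Safety Analysis Set subjects who entered the phase. Its programming note reads: "Reasons for Early Termination from Monitoring Phase and Completion of Monitoring Phase will be pulled from the Study Completion eCRF". SAP 6.6.2 also plans a by-subject listing of semen data with the reversing measurement flagged.

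**The concern.** The rule that defines the event and the displays that report it work at different levels. A man who enters the Monitoring Phase with low concentration and low motility appears in two tables, and neither shows whether he has met the definition.

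The Table 6-3 layout also removes a man from the visit denominator once the tabulated parameter has first crossed the line. He stays in follow-up until all his parameters qualify, so his later concentration values exist but can no longer change the concentration count. He could be counted as reversed for concentration at one visit and for motility at the next without both being above the line at the same visit.

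Men with several affected parameters are the ones for whom the distinction matters. Reversibility is a named part of the second interim analysis (SAP 2.4), which is run at FDA request, and the protocol plans publication of those data.

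**Working it through.** **1. The plan's own figures.** In Table 6-3, cumulative rate = cumulative reversals / men with the decrease.
- Filgotinib: 3/5 = 60.0%, 4/5 = 80.0%, 5/5 = 100.0%, 5/5 = 100.0%. All reproduce.
- Placebo: 3/6 = 50.0%, 4/6 = 66.7%, 5/6 = 83.3%, 5/6 = 83.3%. The second cell is printed as 68%, a slip in a hypothetical example with no bearing here.
- Visit denominators run 5, 5−3 = 2, 2−1 = 1, 1−1 = 0 (filgotinib) and 6, 6−3 = 3, 3−1 = 2, 2−1 = 1 (placebo). This confirms that a man leaves the table at his first crossing.

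**2. Direction for men with two or more decreases.** Recovering on all parameters implies recovering on each one. Among such men the all-parameter rate is therefore at most their lowest per-parameter rate. For men with one decrease the two rates are identical.

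**3. Size for a man with two decreases.** The documents give no recovery rates, no correlation between parameters and no share of men with several decreases. Everything here is an assumption: four Monitoring visits (52/13 = 4), and a chance p at each visit that a parameter is above the line (or, in the persistent case, first crosses it).

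- Per-parameter cumulative rate: 1 − (1−p)^4.
- All-parameter rate, visits independent, correlation 0: 1 − (1−p²)^4.
- All-parameter rate, recovery persistent once reached, correlation 0: [1 − (1−p)^4]².

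| p | Per parameter | All parameters, visits independent | All parameters, recovery persists |
|---|---|---|---|
| 0.3 | 76% | 31% | 58% |
| 0.5 | 94% | 68% | 88% |
| 0.7 | 99% | 93% | 98% |

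For p = 0.5: 1 − 0.5^4 = 0.9375; 1 − 0.75^4 = 0.684; 0.9375² = 0.879.

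Positive correlation narrows the gap. With independent visits and p = 0.5, take a bivariate normal with correlation ρ. The chance that both parameters are above the line at one visit is then 1/4 + arcsin(ρ)/(2π), which is 0.333 at ρ = 0.5 and 0.398 at ρ = 0.8. The all-parameter rates are 1 − 0.667^4 = 80% and 1 − 0.602^4 = 87%. A simulation of 200,000 men gave the same values.

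**4. Effect on an overall percentage.** Treat reversal as a settled yes or no with p = 5/6 for every parameter, the placebo figure in Table 6-3. For a man with two decreases the all-parameter rate lies between 2p − 1 = 66.7% and p = 83.3%, and is p² = 69.4% under independence. If a share f of men have two decreases, the overall rate is (1−f)p + f × (joint rate):
- f = 10%: 81.7% to 83.3%
- f = 25%: 79.2% to 83.3%
- f = 50%: 75.0% to 83.3%

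**5. The direction does not extend to the whole phase.** Suppose 3 of 6 men with a concentration decrease reverse, and 4 of 4 men with only a motility decrease reverse. The subject-level rate is 7/10 = 70%, above the 3/6 = 50% in the concentration table.

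**The case against.** A reader might infer that the endpoint is never produced, or that the tables make recovery look better across the study. The documents support neither.

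- **A subject-level count exists.** The SAP 4.1 category is the number and percentage of men entering the phase who met the criteria on all qualifying parameters. Protocol 6.11 bases exit from the Monitoring Phase on the mean of two semen samples, so the eCRF status should reflect the semen rule. This stands. What remains is that the count is disposition output read from a form, is not linked to the endpoint, and shows no split by Monitoring visit in the text available. Part of SAP 4.1 is missing from that text, so the table columns cannot be checked.
- **The listing shows each man's course.** With numbers as small as the 5 and 6 in Table 6-3, a reader could work out each man's status. That is true, but it leaves the derivation to the reader.
- **The defined term may already apply.** If meeting reversibility criteria in 6.6.2 carries the all-parameter definition from 3.2, a man is not counted until everything has returned. The Table 6-3 title, which is specific to concentration, points the other way. The wording is ambiguous, and the ambiguity reaches the completers table at the interim analysis and the listing flag.
- **Per-parameter tables are correct for their parameter.** An unrecovered motility decrease still shows in the motility table, and display by parameter is prespecified in Protocol 8.5.3. The SAP is therefore following the protocol. The protocol's own analysis section has the same mismatch with its endpoint.
- **The larger gaps need visits to be independent.** No document supports that assumption. With persistent recovery they shrink to 94% against 88% at p = 0.5, and 76% against 58% at p = 0.3.

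**Conclusion.** The point holds in a limited form. The reversibility analysis in Protocol 8.5.3 and SAP 6.6.2 specifies per-parameter tables, while the definition and endpoint are per subject. The all-parameter rate by Monitoring visit, treatment group and week of decrease is not specified there, and it cannot be assembled from the parameter tables.

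For men with two or more decreases, those tables show a rate at least as high as the defined one. The size of the difference depends on recovery rates, correlation and persistence that the documents do not give; the figures above are illustrations. SAP 6.5.3 provides a row for a concentration decrease combined with a motility and/or morphology decrease, but that does not show how many such men there will be. If none occur, there is no numerical difference.

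The endpoint is exploratory and SAP 6.6.2 plans no test or confidence interval, so no error rate or power is affected. Severity is minor.

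**What to change.** Add one subject-level cumulative table to SAP 6.6.2 in the Table 6-3 layout.
- **Denominator:** subjects who entered the Monitoring Phase.
- **Event:** the first Monitoring visit at which all of a man's qualifying parameters exceed 0.5 × baseline at that same visit, derived from the semen data.
- **Groupings:** those already in 6.6.2. Week 13 decreases by double-blind treatment, Week 26 decreases by treatment sequence and responder status, and decreases at or after Week 39 by treatment sequence.
- **Role:** this table displays the exploratory endpoint, and the per-parameter tables become supportive.

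State which rule, per-parameter or all-parameter, governs each table, the completers definition and the listing flag.

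The cost is one more table from data already collected and a few sentences of SAP text, with no change to study conduct. If it is added after SAP finalization, record it in the clinical study report, as SAP Section 1 requires. The reported reversibility percentage for men with several decreases may be less favourable than the parameter tables suggest.

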In case a subject needs to be treated with a prohibited medication (see Table 5.1 from the study protocol), for instance to control their rheumatic condition, the subject will discontinue the study and complete an Early Termination (ET) visit (including semen collection). For subjects on filgotinib, this will be followed by a safety follow-up visit 30 days after last study drug dose.

All subjects who did not enter the Monitoring Phase will continue the study until the Week 156 visit.

Monitoring Phase (up to 52 weeks)

Subjects whose semen parameters meet any of the pre-specified sperm decrease thresholds will switch to the Monitoring Phase immediately. Subjects on double-blind treatment or open-label filgotinib who enter the Monitoring Phase will discontinue study drug and start Standard of Care. These subjects will also have a safety follow-up visit 30 days after the last study drug dose. Subjects on Standard of Care in the extension phase will continue taking a Standard of Care regimen in the Monitoring Phase.

All subjects who enter the Monitoring Phase will undergo semen evaluations every 13 weeks starting from their entry into the Monitoring Phase, for up to 52 weeks or until reversibility (defined as a return to $> 0.5 \times$ [mean of 2 evaluable samples collected at screening visit] for all sperm parameter[s] qualifying the subject for the monitoring phase—based on 2 evaluable samples collected at the monitoring phase visit) is met, whichever is achieved first.

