3. GENERAL CONSIDERATIONS FOR DATA ANALYSES

Analysis results will be presented using descriptive statistics. For categorical variables, the number and percentage of subjects in each category will be presented; for continuous variables, the number of subjects (n), mean, standard deviation (SD) or standard error (SE), median, first quartile (Q1), third quartile (Q3), minimum, and maximum will be presented.

All statistical tests will be 2-sided and performed at the 5% significance level unless otherwise specified.

By-subject listings will be presented for all subjects in the All Randomized Analysis Set and sorted by subject ID number, visit date, and time (if applicable). Data collected on log forms, such as AEs, will be presented in chronological order within the subject. The treatment group to which subjects were randomized, double-blind treatment and responder/non-responder status at Week 13, or treatment sequence will be presented in the listings, as appropriate. Age, sex, race, ethnicity, start and end date of the double-blind study drug and open-label filgotinib or start and end date of extension phase (for subjects who were switched to standard of care in the extension phase) will be included in the listings, as space permits. A by-subject listing will be provided for subjects with any visits or assessments impacted by Coronavirus Disease 2019 (COVID-19).

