6.5. Other Displays of Sperm/Semen Data

6.5.1. Week 26 by Treatment Sequence and Responder/Non-Responder at Week 13 Displays

Displays will be presented at the Week 26 visit for the following 4 groups:

- filgotinib responder at Week 13 switched to open-label filgotinib
- filgotinib non-responder at Week 13 switched to standard of care
- placebo responder at Week 13 switched to standard of care
- placebo non-responder at Week 13 switched to standard of care

The number and proportion of subjects with a $\geq 50\%$ decrease from baseline in sperm concentration at the Week 26 visit will be presented. An exact 95% CI for the proportion of subjects with a $\geq 50\%$ decrease from baseline in sperm concentration at Week 26 within treatment sequence and responder/non-responder status group will be presented based on the Clopper-Pearson method.

For all secondary continuous endpoints, 8-point summary statistics (n, mean, SD, median, Q1, Q3, minimum, and maximum) by treatment sequence and responder/non-responder status at Week 13 will be provided for the value at the visit, change from baseline, and percentage change from baseline in sperm/semen parameters at Week 26. A 95% distribution-free CI on the median change and percentage change from baseline at Week 26 in all sperm/semen parameters will be constructed by treatment sequence and responder/non-responder status at Week 13 using the CIPCTLDF option in PROC UNIVARIATE in SAS.

A cumulative distribution plot for percentage change from baseline in sperm concentration at Week 26 will be constructed by treatment sequence and responder/non-responder status at Week 13 for those who remain on study drug at the Week 26 visit.

6.5.2. Treatment Sequence Displays at/after Week 39

Displays will be presented by analysis visit at Week 39 and thereafter in the Extension Phase for the following 3 treatment sequences:

- filgotinib to open-label filgotinib
- filgotinib to standard of care
- placebo to standard of care

The number and proportion of subjects with a $\geq 50\%$ decrease from baseline in sperm concentration will be presented by analysis visit.

For all secondary continuous endpoints, 8-point summary statistics (n, mean, SD, median, Q1, Q3, minimum, and maximum) by treatment sequence will be provided for the value at the visit, change from baseline, and percentage change from baseline in sperm/semen parameters.

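### Reversibility is reported as counts and percentages with confidence intervals ruled out, so the plan leaves unstated how little a small, all-reversed group can exclude

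*SAP*

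**What the plan says.** SAP 6.6.1 lists reversibility as one of two exploratory endpoints ("Percent of reversibility among subjects who experience a" decrease of at least 50% in concentration, motility or morphology). The other is change in hormones.

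For the display, SAP 6.6.2 says: "The number (percent) who met reversibility criteria and the cumulative number (percent) who met reversibility criteria at each Monitoring Phase visit will be presented". Each sperm parameter is summarised separately. Men who qualify at Week 13 are shown by double-blind arm. The rest are shown "at Week 26 by treatment sequence and responder/non-responder at Week 13; and at/after Week 39 by actual treatment sequence". A by-subject listing flags the measurement at which reversibility was met. On precision, the section says only: "No formal testing or CI is planned".

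Protocol 8.5.3 is consistent with this. It asks that "the number and percentage and cumulative number and percentage of subjects who achieve reversibility will be displayed by sperm parameter and monitoring phase visit" and mentions no interval.

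Elsewhere the SAP does attach intervals to small-group summaries. In SAP 6.5.1 the Week 26 proportion with a sperm-concentration decrease of at least 50% gets an exact 95% interval "within treatment sequence and responder/non-responder status group will be presented based on the Clopper-Pearson method". In SAP 6.6.3 the hormone changes get distribution-free intervals on medians and quantile-regression intervals on the arm difference.

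**The concern.** Reversibility is the question for which the Monitoring Phase exists. The second interim analysis is defined by completion of reversibility follow-up (protocol, Definition of Terms; SAP 2.4, which says the FDA requested it), and its publication is planned (protocol 8.11). The background makes the answer matter. Protocol 1.2.2.4 reports that testicular toxicity in animals was only partly reversible and that sperm counts stayed low. Protocol 1.4 says that subjects consent to a risk of possibly permanent infertility.

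For such a question, the useful statement is often not the percentage that reversed but the percentage of non-reversal that the data can exclude. A count and percentage do not state that. With few men in a group, 100% reversed can look conclusive when it is not. The SAP already uses the method that would show this, in groups split the same way.

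**Working it through.** **Inputs.** The illustrative counts are from SAP Table 6-3, which is labelled hypothetical. The interval method is the Clopper-Pearson method of SAP 6.5.1. The level follows SAP section 3: "All statistical tests will be 2-sided and performed at the 5% significance level unless otherwise specified", hence two-sided 95% intervals. The documents give no actual reversibility denominators, so a range of group sizes is shown.

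**Step 1: reproduce Table 6-3.** Filgotinib cumulative rates are 3/5 = 60.0%, 4/5 = 80.0% and 5/5 = 100.0%. Placebo rates are 3/6 = 50.0% and 5/6 = 83.3%. All match. One cell does not: placebo 4/6 is 66.7%, and the table prints 68%.

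**Step 2: exact interval.** For x reversed of n, the lower limit is the 0.025 quantile of Beta(x, n − x + 1) and the upper limit is the 0.975 quantile of Beta(x + 1, n − x). When x = n the lower limit reduces to 0.025^(1/n) and the upper limit is 100%.

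- 5/5: 0.025^(1/5) = 0.478, so 47.8% to 100%. Check: 0.5^5 = 0.031, which exceeds 0.025, so a true rate of one half lies just inside the interval.
- 5/6: 35.9% to 99.6%.

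**Step 3: all-reversed groups over a range of sizes.**

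| Reversed / n | Exact 95% lower limit |
|---|---|
| 1/1 | 2.5% |
| 2/2 | 15.8% |
| 3/3 | 29.2% |
| 4/4 | 39.8% |
| 5/5 | 47.8% |
| 6/6 | 54.1% |
| 8/8 | 63.1% |
| 10/10 | 69.2% |

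The limit is below one half when n < ln(0.025)/ln(0.5) = 5.3, that is, for n of five or fewer. At 10/10 a true non-reversal rate of up to 100 − 69.2 = 30.8% is still not excluded.

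**Step 4: dependence on method.** For 5/5 the lower limit is 56.6% by Wilson, 62.1% by Jeffreys, 51.1% by Agresti-Coull and 54.9% by the one-sided 95% exact limit. All four are above one half. For 3/3 every two-sided method is below one half (exact 29.2%, Wilson 43.9%, Jeffreys 46.4%, Agresti-Coull 38.3%).

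**Step 5: how finely the data are split.** There are two groups for Week 13 entrants, four for Week 26 entrants and three for later entrants, so nine groups. With three sperm parameters that is up to 9 × 3 = 27 cells. How many men fall in each cannot be derived from the documents.

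**The case against.** The best case for the plan is that this is an open, pre-specified descriptive choice for an exploratory endpoint, and that it follows protocol 8.5.3. Several parts of that case stand.

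- **Counts are shown.** A reader might infer that only a percentage will appear. That is not so: numerators and denominators accompany the percentages, and there is a by-subject listing. Anyone can compute the interval from them.
- **Reversibility is not singled out.** The proportions in SAP 6.5.2 (Week 39 onward) and SAP 6.5.3 (decrease thresholds and semen abnormalities) get no interval either. The Week 26 proportion that does get one is a secondary endpoint.
- **Table 6-3 is invented.** A reader might infer from 100.0% against 83.3% that the trial's denominators are five and six, or that the display favours filgotinib. The table is labelled hypothetical and supports neither inference.
- **No overclaim is planned.** Neither document says that the table will be used to assert full reversibility, and no between-arm comparison is planned.
- **Pooling may help.** SAP 1.3 plans pooling with the sister study, and protocol 8.12 refers to a separate integrated SAP. That document is not available, so whether it gives reversibility intervals cannot be judged.

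These points limit the finding but do not remove it. Exploratory status does not explain the omission, since the other exploratory endpoint has intervals. An interval is not a test, so ruling out testing does not require ruling out intervals. A safety conclusion should also not depend on readers computing its precision for themselves.

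**Conclusion.** The point holds as a cheap improvement to the presentation, not as an error in the plan. SAP 6.6.2 excludes an interval that the SAP's own practice in 6.5.1 would supply, for the question on which the second interim analysis depends.

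The size depends on denominators that are unknown. If groups are small, an all-reversed result leaves a true reversal rate as low as 47.8% (n = 5), 54.1% (n = 6), 63.1% (n = 8) or 69.2% (n = 10) compatible with the data. These figures assume the two-sided exact method and the 95% level.

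It is tempting to go further and say that a small all-reversed group is compatible with fewer than half reversing. That is true only for five men or fewer under this method. At exactly five it is a near-threshold result that the other intervals tried do not reproduce. What does not depend on that threshold is the general statement: a handful of men, all of whom reversed, does not establish full reversibility.

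**What to change.** Replace the sentence in SAP 6.6.2 with text to this effect:

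> No hypothesis test is planned for reversibility. For each sperm parameter, the final cumulative proportion will carry an exact (Clopper-Pearson) two-sided 95% CI within the groups already displayed: Week 13 entrants by double-blind arm, Week 26 entrants by sequence and Week 13 response, and entrants at or after Week 39 by sequence.

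This keeps the statement that nothing is tested. It also names the groups, so that men who qualified on blinded drug, open-label filgotinib and standard of care are not pooled by default. SAP section 1 has changes after finalisation documented in the CSR, so the addition can be recorded there and labelled as such. In the same edit, correct 4/6 in Table 6-3 to 66.7%.

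The cost is one sentence and one column. It needs no new data and changes nothing in conduct. The downside is a set of wide intervals on an exploratory endpoint. Point estimates are unchanged.
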